6 STUDY INTERVENTION

6.1 STUDY INTERVENTION(S) ADMINISTRATION

6.1.1 STUDY INTERVENTION DESCRIPTION

The investigational product (IP), 'Airmod', manufactured by Heroic Faith Medical Science Co., Ltd., is intended to provide professionally trained health professionals with continuous non-invasive measurement and monitoring of respiratory rate in adult patients. It is designed to detect inhalation acoustics and provides respiratory rates based on the analysis of the acoustic signals of breathing sounds collected by the electronic stethoscope. The device is intended for use in hospitals, hospital-type facilities, during intra-hospital transport, and out-of-hospital emergency medical service (EMS) applications that include ground and air transport. The intended for use is further described in 10.2.5.

In this study, Airmod will be used along with AS-101 (AccurSound Electronic Stethoscope, a commercially available device in Taiwan). There are no known contraindications and are not designed for use in patients unable to be assessed by stethoscope such as who require the use of high-flow nasal cannula.

Table 1 and 2 provides a list of devices and accessories components that may be used in the study.

Table 1. Airmod and Accessory Components

Product	Model or Version or Material
Airmod Software	Airmod V1
Additional Accessories	Devices with operating system standard Android 10/11, RAM 8G, 128G; chipset processing power equivalent or superior to Snapdragon™ 855.
	AccurSound Electronic Stethoscope model AS-101 (herein referred to 'AS-101')
	Surgical tape

Table 2. Capnostream™35 Devices and Accessory Components

Product	Model or Version or Material
Hardware (monitor)	Capnostream™35 Portable Respiratory Monitor PM35MN
Capnostream™35 Software	Monitor: 01.00.06.05 CO ₂ : 01.14
Unit dimensions	(Height) 213 mm × (Width) 137 mm × (Depth) 55 mm
Power supply	Input Voltage 100-240 V, 50/60 Hz, ± 10%
Waveform sampling rate	20 samples/sec
Additional Accessories	'Medtronic' Microstream™ etCO ₂ Sampling Lines (Smart CapnoLine Plus O ₂ , herein referred to 'sampling lines')

6.1.2 DOSING AND ADMINISTRATION

Subjects will be monitored with the devices Airmod and Capnostream™35 simultaneously on Visit 2; both devices should be ready and apply correctly on the subject before sedation.

- Airmod administration procedure

Preparation

1. The device with Airmod should have enough battery life that last for the whole study process. Attach the device with Airmod with the AS-101 using type- C to type-C cable.
2. Place the auscultation sensor on the patient neck (left or right-side plain area of thyroid cartilage), secure with surgical tape.
3. Click on the 'Airmod' on the screen of the device to enter the software interface. When the device with Airmod and AS-101 are properly connected, an indicator light should come up, and then are able to click on the start/stop button to start monitoring.
4. By clicking the start/stop button, immediately breathing sound and spectrogram should be presented via speaker and display screen respectively, and if the signal or reception is unstable, adjust the auscultation sensor or secure with surgical tape to improve.

Monitoring (start time)

5. To start recording the monitoring for the study, on the display screen, select start/ stop button and entering the patient ID.

Monitoring (end time)

6. To end monitoring and terminate the saving process, on the display screen, select the start/stop button. This procedure should be done at the time point where the subject is ready to discharge from post anesthesia care unit (PACU) or the end of non-anesthesia period, which compliance with the criteria PAR or PADSS score ≥ 9 or determined termination by principal investigator.

- Capnostream™35 administration procedure

Preparation

1. Capnostream™35 should have enough battery life that last for the whole study process.
2. To set up for the subject, on the monitoring display screen, select menu -> action -> patient admin -> insert the subject number.
3. Connect the sampling line to the monitor, rotate it clockwise until it can no longer be turned; and also connect the sampling line to the subject nostril, adjust the tightness at the lower band to fit on the subject. When properly connected, the monitor will immediately begin to search breaths, then present EtCO_2 value and waveform on the display screen after 3.4 ~ 5.0 second.
4. Connect the pulse oximetry line to the monitor and clip the pulse oximetry probe onto the finger of subject. When properly connected, the monitor will present SPO_2 value on the display screen after 3.4 ~ 5.0 second.
5. To start storing the report and output to SD card, on the monitoring display screen, select menu -> report -> store report -> real-time full continuous transfer -> choose to save in SD card or USB drive -> save report.

Monitoring (start time)

6. The monitoring period starts once the last step (save report) has been done.

Monitoring (end time)

7. To end monitoring and terminate the saving process, on the monitoring display screen, select menu -> report -> store report -> active report -> stop. This procedure should be done at the time point where the patient is ready to discharge from PACU or the end of non-anesthesia period, which compliance with the criteria PAR or PADSS score ≥ 9 or determined termination by principal investigator.

The administered anesthetic medication and dosage, surgery type, start and stop time of surgery will be collected during surgery.

The medical records of subjects will be confirmed on allowed visit window (within 14 days).

6.2 PREPARATION/HANDLING/STORAGE/ACCOUNTABILITY

6.2.1 ACQUISITION AND ACCOUNTABILITY

The investigator and study staff will be responsible for the accountability of all clinical supplies (dispensing, inventory, and record keeping) following the Sponsor's instructions. In this matter, the investigator and study staff must adhere to GCP guidelines, as well as national requirements. Under no circumstances will the investigator allow the investigational product to be used other than as directed by this protocol. Clinical supplies will be dispensed only by an appropriately qualified person and will not be dispensed to any individual who is not enrolled in the study. An accurate and timely record of the receipt of all clinical supplies and dispensing of investigational product to the subject must be maintained.

The supplies and inventory records must be made available, on request, for inspection by the Sponsor (or its designee) or a representative of a regulatory authority. All unused investigational product is to be returned to the Sponsor at the conclusion of the study, unless provision is made by the Sponsor for destruction of supplies at the study site. On completion of investigational product accountability and reconciliation procedures by study site personnel and documentation procedures by Sponsor personnel, investigational product that is to be returned to the Sponsor, if necessary, must be boxed and sealed and shipped back to the Sponsor following all local regulatory requirements.

6.2.2 FORMULATION, APPEARANCE, PACKAGING, AND LABELING

The investigational materials will be obtained and/or packaged and labeled in a manner consistent with the study design including but not limited to product name, model number, lot number, quantity, shelf life, manufacturing date, company name, company address, manufacturer name and manufacturer address.

Labels will be non-removable in nature. Sample labels for the primary package containing the investigational products are including but not limited to product name, model number, material, lot number, quantity, shelf life, manufacturing date, company name, company address, manufacturer name, manufacturer address, study number and storage condition.

6.2.3 PRODUCT STORAGE AND STABILITY

The investigational product will be stored in accordance with labelled storage conditions. The investigation products (IPs) must be kept strictly separate and in a different location than non-study

commercially available product. The IP should be kept at 0°C to 40°C (32°F to 104°F) and humidity level 15% to 90% until time of use. No damage should appear on the packaging and/or device before using.

Temperature monitoring is required at the storage location to ensure that the investigational product is maintained within an established temperature range. The investigator is responsible for ensuring that the temperature is monitored throughout the total duration of the study and that records are maintained; the temperature should be monitored continuously by using either an in-house validated data acquisition system, a mechanical recording device, such as a calibrated chart recorder, or by manual means, such that minimum and maximum thermometric values over a specific time period can be recorded and retrieved as required.

6.2.4 PREPARATION

Set up for the device with Airmod and Capnostream™35 is required, manual book and a quick guild card along with the product information will be provided for the user included in the study training materials. The device data transfer process will be tested and verified during the site initiation process.

6.3 MEASURES TO MINIMIZE BIAS: RANDOMIZATION AND BLINDING

This study will not be randomized and blinded.

6.4 STUDY INTERVENTION COMPLIANCE

Records of treatment administration for each subject will be kept during the study.

6.5 CONCOMITANT THERAPY

Not applicable in this study.

6.5.1 RESCUE MEDICINE

Not applicable in this study.

7 STUDY INTERVENTION DISCONTINUATION AND PARTICIPANT DISCONTINUATION/WITHDRAWAL

7.1 DISCONTINUATION OF STUDY INTERVENTION

If subject discontinued without administered study intervention, no further evaluations are needed.

7.2 PARTICIPANT DISCONTINUATION/WITHDRAWAL FROM THE STUDY

Participants are free to withdraw from participation in the study at any time upon request.

An investigator may discontinue or withdraw a participant from the study for the following reasons:

- Participant unable to receive Airmod and/or Capnostream™35 and their device related accessories.
- After adjustment, noises (such as those caused by air leak continue to pronounce-affect signal quality) continue to be pronounced, and cannot be resolved.
- The anesthesiologists determine that the participant is at risk of hypoxemia or other life-threatening conditions.
- If any clinical adverse event (AE), laboratory abnormality, or other medical condition or situation occurs such that continued participation in the study would not be in the best interest of the participant.

The reason for participant discontinuation or withdrawal from the study will be recorded on the Case Report Form (CRF). Subjects who signed the informed consent form (ICF) and subsequently withdraw, or discontinued from the study, will not be replaced.

7.3 LOST TO FOLLOW-UP

Not applicable in this study.

8 STUDY ASSESSMENTS AND PROCEDURES

8.1 EFFICACY ASSESSMENTS

During the study visit 2 (Day 1), the breathing sound and partial pressure of CO₂ will be recorded using the device with Airmod and Capnostream™35 respectively. The breathing sounds is obtained from the device with Airmod as a wav file, while the partial pressure of CO₂ (with sampling rate of 20 Hz) is obtained from Capnostream™35 as a txt file.

Accurate time frame is required as is the factor which may affect the endpoint. Both devices should start and end the recording at the same time in a specific time point, as below.

- Non-Anesthesia Stage: Up to 40 patients will be randomly assigned to non-anesthesia stage assessment, the measurement will be evaluated after enrollment with ICF, at the NOR area. (5~30 minutes)
- Procedure Stage: From firstly anesthetic administration to end of procedure. (Depends on procedure 10mins ~ few hours)
- NORA stage: From transportation of subjects to PACU to discharge from PACU (PAR or PADSS score ≥ 9) (Ideally keep following to 15 minutes)
 - Post Anesthesia Recovery (PAR) score

The information of patient monitoring period refers to 10.2.1.

The Post Anesthesia Recovery (PAR) score (Miller's Anesthesia, 9th Edition) will be performed and recorded by relevant personnel after the transfer of care through the PACU. Subjects are evaluated upon admission and every 15 minutes until a score of ≥ 9 is reached. Elements include:

Activity	Muscle activity is assessed by observing the ability of the patient to move his/ her extremities spontaneously or on command.
Respiration	Respiratory efficiency evaluated in a form that permits accurate and objective assessment without complicated physical tests.
Circulation	A measurement of cardiovascular homeostasis and a comparison with previous blood pressures.
Consciousness	Determination of the patient's level of consciousness.
Oxygen saturation	Measurement of arterial oxygen saturation using pulse oximetry.

- Post Anesthesia Discharge Scoring System (PADSS)

The Post Anesthesia Discharge Scoring System (PADSS) (Miller's Anesthesia, 9th Edition) will be performed and recorded by relevant personnel after the transfer of care through the PACU. Subjects are evaluated upon admission and every 15 minutes until a score of ≥ 9 is reached. Elements include:

Vital signs	A measurement of cardiovascular homeostasis and a comparison with previous blood pressures.
Activity level	Prior to discharge home, the patient's activity level must be at baseline. Patient must be able to ambulate at preoperative level.
Nausea and vomiting	Prior to discharge, the patient must have minimal to no nausea and vomiting.
Pain	Pain/discomfort must be at a level identified by the patient as tolerable. The location, type and intensity of pain should be consistent with anticipated postoperative discomfort.
Surgical bleeding	The surgical site must be free from excessive or unexpected bleeding/ drainage.

The breathing sounds and the partial pressure of CO₂ will then convert to the breathing counts and CO₂ waveform respectively using self-developed software written from Python and Matlab, the data will be recorded in Microsoft Excel and RR will eventually be calculated manually by trained personnel for each result.

During the study, if the study staff indicates the breathing sounds or the partial pressure of CO₂ is affected, for instance, an obviously external sound, moving the patient, nasal cannula drop, blocked, or other situation identify by the investigator. Such start/stop time of event(s) will be recorded in CRF, accurate to second. Such affected data or missing data will be excluded in the final comparison as such event(s) may be affecting the study result, determined by the investigator during the monitoring period.

8.2 SAFETY AND OTHER ASSESSMENTS

- Safety Assessment

The adverse events will be reviewed and evaluated by investigator throughout the study period (after enrollment to end of study). All adverse events will be recorded on the CRF.

- Medical History

A complete medical history will be reviewed at Screening. Medical history within 3 months prior to Screening will be recorded. Medical conditions occurring more than 3 months prior to Screening will not be recorded, unless they are judged by the principal investigator(s) to be significant.

- Demographic Data

Demographic information for each participant, including birth date and gender will be collected and recorded at Screening.

- Physical Examination

A full physical examination will be performed at Screening. Items will include: general appearance, weight and height, HEENT (head, eyes, ears, nose, and throat), mouth, skin, neck (including thyroid), lymph nodes, spine, cardiovascular system, respiratory system, gastro-intestinal system, nervous system, musculoskeletal system, blood and blood forming organs, mental status, and other body systems if applicable for describing the status of participant's health.

- Vital Signs

Vital signs include body temperature (°C), blood pressure (including systolic and diastolic blood pressure, unit: mmHg), and pulse rate (times/minute) will be performed at Screening. Results will be documented in the CRF. Vital signs should be evaluated after the participant has rested in a sitting position for at least 3 minutes. Note that study site staff should measure ear temperature of the participant if possible. If tympanic or axillary methods are used, the same method should be used consistently throughout the study.

9 STATISTICAL CONSIDERATIONS

9.1 STATISTICAL HYPOTHESES

Primary Analysis:

In this study, all the measurements were conducted in the same subject, and the clocking variance would be limited by investigator justification procedure to acquire the utmost matching recording. The study design is a paired non-inferiority test to evaluate accuracy and performance of respiratory rate (RR) measurement from Airmod compared to Capnostream™35. The primary objective is to establish the non-inferiority. The primary end goal is to test the entire effect at the margin of 3 breaths per minute (bpm). The non-inferiority is a directional (one-sided) test. The null hypothesis (H_0) and alternative (H_1) are defined as:

$$H_0: \mu_{\text{AirRR}} - \mu_{\text{ManCRR}} < -3; \\ H_1: \mu_{\text{AirRR}} - \mu_{\text{ManCRR}} \geq -3.$$

Details refer to the SAP.

9.2 SAMPLE SIZE DETERMINATION

By referencing predicate device clinical trials on respiratory rate monitoring in the hospital setting, most of the cases recruited 120+ patients. Considering a 40% withdrawal/dropout rate, we proposed a total enrollment of 300 subjects.

Details refer to the SAP.

9.3 POPULATIONS FOR ANALYSES

The analysis will test the performance and safety using the Per-Protocol (PP) and Intention-to-Treat (ITT). The PP population is defined to be evaluable subjects who complete the entire study procedure without major protocol violations. The ITT population is defined to be all treated subjects who are administered using the device with Airmod and Capnostream™35.

Details refer to the SAP.

9.4 STATISTICAL ANALYSES

Details refer to the SAP.

9.4.1 GENERAL APPROACH

For descriptive statistics, continuous variables will be presented as N, mean, median, SD, maximum and minimum, while categorical variables will be presented as N and percentiles.

9.4.2 ANALYSIS OF THE PRIMARY EFFICACY ENDPOINT(S)

In this study, all the measurements were conducted in the same subject, and the clocking variance would be limited by investigator justification procedure to acquire the utmost matching recording. The study design is a paired non-inferiority test to evaluate accuracy and performance of respiratory rate (RR) measurement from Airmod compared to Capnostream™35. The primary objective is to establish the non-inferiority. The primary end goal is to test the entire effect at the margin of 3 breaths per minute (bpm). The non-inferiority is a directional (one-sided) test. The null hypothesis (H0) and alternative (H1) are defined as:

$$\begin{aligned} H_0: \mu_{\text{AirRR}} - \mu_{\text{ManCRR}} &< -3; \\ H_1: \mu_{\text{AirRR}} - \mu_{\text{ManCRR}} &\geq -3. \end{aligned}$$

At the interim analysis, under 99.69% CI, when reject the null hypothesis (H0) indicates the non-inferiority.

At the final analysis, under 95.1% CI, when reject the null hypothesis (H0) indicates the non-inferiority.

A subgroup analysis for those subjects with $\text{BMI} \geq 30$ will follow the original study design in a stratified sample pool to test the non-inferiority at the margin of 3 bpm.

According to 7.2, part of the measurement result within subject will be censored and excluded in the paired non-inferiority test. The principle of exclusion is based on the investigator reported failure event/period of Airmod or Capnostream™35, the report will be confirmed by the principal investigator. The data prior to discontinuation or following a fixed machine failure period will be included in the paired non-inferiority test.

9.4.3 ANALYSIS OF THE SECONDARY ENDPOINT(S)

[figure not shown]
1. To assess the accuracy of respiratory rate measurement by Airmod in comparison with manual-scored auscultation sound during the less sensitive period of Capnography on Capnostream™35, the accuracy of inhalation classification in the segmentation basis is greater than 82.5% at the 95% CI. The performance metrics (F1-score, MAPE) at event level will be demonstrated and target for F1-score > 0.8, MAPE < 0.5.

The precision and recall rate of Airmod deep learning machine, the F1-score build up and bind the hierarchy positive and negative metrics all together. It is generally described the harmonic mean of the two. Besides, the MAPE enhanced the difference power of error prediction by keep positive and negative errors from cancelling out each other. The relative errors are independent with the scale of target.

F1-score:

$$F - score = \frac{(1 + \beta^2) \text{precision} \times \text{recall}}{\beta^2 \text{precision} + \text{recall}}$$

MAPE:

The output size of our model is a 235×1 vector for a 15-second audio recording so that the duration of each time frame is about 0.064 second. During the inference process, the deep learning model determines whether a time frame belongs to an inhalation. After comparing the inference results with the manual-scored ground-truth labels, we can assign true positive (TP), false positive (FP), true negative (TN), or false negative (FN) to each time frame. Thus, the accuracy $((TP+TN)/(TP+TN+FP+FN))$ of inhalation detection in the segment level can be calculated. We use the accuracy of segment detection to evaluate the performance of the deep learning model.

2. To measure the agreement of AirRR and ManCRR on concordance correlation coefficient, and on their mean and bias by Bland-Altman analysis.

Bland-Altman analysis is used to measure the consistency of continuous data from two distinct measurements. Therefore, the likelihood of AirRR and ManCRR will be quantified and visualized on the assumption of fixed observer and pairs Bland-Altman analysis. It combines the quantitative analysis of LoA (limits of agreement) and the qualitative analysis of scatter plot to show an instinctive evaluation between two methods of their correlation. Each of the n samples is then represented on the graph by assigning the mean of the two measurements as the x-value, and the difference between the two values as the y-value. By this graphical method, we can extend a simple logarithmic transformation approach to data where there is a relationship between difference and magnitude. We discuss the importance of repeatability of RR measurements from each equipment and compare an estimate of this to the LoA. [20] In this case, if the difference of RR measured from two equipment are in the 95% LoA, we will say that RR measured from these two equipment are correlated and acceptable.

$$S(x, y) = \left(\frac{\Delta G_A + \Delta G_E}{2}, \Delta G_A - \Delta G_E \right)$$

3. Use paired t-test to compare the response time of Airmod versus Capnography on Capnostream™35 after administration of jaw thrust. In the target of $p<0.05$ indicates significance. The principal investigator and research members will determine the apnea period and the first effective breath.

The paired t test can be used when the two groups under comparison are dependent on each other. [21] By acquiring the T value from paired t-test, we can obtain the p value indicating the significant difference level via t-distribution table or Microsoft Excel. A p value less than 0.05 would indicate that Airmod is able to resume RR estimation after proper intervention faster than Capnostream™35.

$$t = \frac{\bar{X}_1 - \bar{X}_2}{\sqrt{\frac{(s_1^2 + s_2^2)2\rho s_1 s_2}{n}}}$$

4. Capnography is inherently limited in certain circumstances which may cause ineffectively detecting CO₂, including movement, nasal cannula drop, blocked, or other situations. Airmod is superior to capnography in these limitations since it detects and measure breath sound directly.

4.1 The difference of ManCRR minus AirRR and ManCRR minus CapRR indicates non-inferiority at margin of 3 bpm (M1) and sampling rate 1Hz.

The difference between ManCRR and AirRR is comparing with the difference between CapRR and ManCRR to indicate the bias of Airmod are non-inferior to the reference devices at the margin of 3 bpm, which also demonstrates substantial equivalence.

4.2 The difference of ManCRR minus AirRR and ManCRR minus CapRR indicates non-inferiority at margin of 2 bpm (M2) and sampling rate 1Hz.

To evaluate whether Airmod can approach a strict standard suggested by clinicians, the difference between ManCRR and AirRR is comparing with the difference between CapRR and ManCRR to indicate the bias of Airmod are non-inferior to the reference devices at the margin of 2 bpm, which indicates the largest clinically acceptable difference.

According to 7.2, part of the measurement result within subject will be censored and excluded in the paired non-inferiority test. The principle of exclusion is based on the investigator reported failure event/period of Airmod or Capnostream™35, the report will be confirmed by the principal investigator. The data prior to discontinuation or following a fixed machine failure period will be included in the paired non-inferiority test.

5. The usability questionnaire as reference [Usability_Airmod] and descriptive analysis will be performed and recorded.

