8.2.5 Bland-Altman analysis

The Bland-Altman analysis is widely used to measure the consistency of continuous data from two distinct measurements. It combines the quantitative analysis of LoA (limits of agreement) and the qualitative analysis of scatter plot to show an instinctive evaluation between two methods of their correlation. Each of the n samples is then represented on the graph by assigning the mean of the two measurements as the x-value, and the difference between the two values as the y-value. The repeatability of RR measurements from Airmod (AirRR) and CapnostreamTM35(K150272, Medtronic) (CapRR) will be compared with ManCRR separately under the sampling rate: 1 sample point per 60 seconds, the differences are representing into Δ G_A and Δ G_E, while the S(x,y)=((Δ G_A+ Δ G_E)/2, Δ G_A- Δ G_E). To compare an estimate of this to the LoA, the two LoA are the mean value of x separately ±1.96SD. (doi: 10.1080/10543400701329422)

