8.6 Treatment Compliance

Not applicable.

9 Efficacy Analyses

To demonstrate the non-inferiority, the Efficacy Analyses included all of the intent to treat population; it followed the objective of study endpoint to measure respiratory rate performance of Airmod (AirRR) in comparison with the reference device (ManCRR and CapRR). The respiratory rate estimation of each device under test (DUT) is described in the unit of the respiratory count per minute from each measurement over time (sampling rate at 1Hz) regardless of actual cause of inhalation event detected by DUT. The efficacy of agreement in the secondary endpoint is evaluated by Bland Altman analysis, a bias between mean and difference, and 99.69% CI at interim analysis and 95.1% at final analysis of the difference between DUTs in an unit difference plot (unit = breaths per minute). Subgroup analysis of each endpoint focuses on various sections and scenarios of anesthesia (from preparation, induction,

interoperation, transportation, and post anesthesia care unit). An obesity group (BMI >=30) is particularly selected to indicate the high risk patients in the procedural sedation and they will be tested as a stratified subgroup in all of the study endpoints.

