The primary efficacy analysis of primary endpoints are comparing the difference of AirRR and ManCRR to reject the null hypothesis (difference of estimation is greater than the non-inferiority limit : -3) under 95% level of confidence interval of all ITT population. The $\mu\alpha$ denotes the respiratory counts of AirRR per minute, and the $\mu\beta$ denotes the respiratory counts of ManCRR per minute. The respiratory count per minute is the mean of recorded samples (eliminating the missing or non-detecting data

point) in each minute. Respiratory counts per minute represent the respiratory rate and are tested in the primary objective hypothesis with the type I error of 0.025, and Type 2 error of 0.2, and the power is 0.8 with single tail non-inferiority analysis.

| Step | Summary |
|-------------------------------|---|
| Objective | Non-inferiority: H0:μα-μβ> d _{NI} vs H1:μα-μβ≤ d _{NI} |
| Endpoint | Margin_1 >-3; Margin_2 >-2 |
| Error | Type I error α=0.025 (one-sided) |
| | Type II errorβ=0.2, Power 1-β=0.8 |
| Non-inferiority limit | d _N = -3 Brpm |
| Population standard deviation | σ=3.29647 |
| Others | r=1, dropout rate=0.3% |

Reference from our pilot study in 25 cases

Table 6. Statistical information referencing from pilot study

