the actual measurement of the respiratory event.

9.2.2 Analysis to measure the agreement between AirRR and ManCRR.

Bland Altman analysis, and concordance correlation is adopted to measure the agreement between AirRR and ManCRR. The quantitative results of respiratory rate from these devices under test over time are evaluated by the above mentioned method to analyze the mean and bias from the plot and concordance correlation coefficient.

Fig 9. Bland Altman between AirRR and ManCRR (Example)

Fig 10. Correlation between AirRR and ManCRR (Example)

Fig 11. Correlation between AirRR and ManCRR during induction period (Example)

Evaluating the Non-Inferiority of Airmod to Capnostream™35 on Respiratory Rate Monitoring and User Experience Clinical Evaluation

Fig 12. Correlation between AirRR and ManCRR during Inter-operation period (Example)

Fig 13. Correlation between AirRR and ManCRR during transportation and PACU period (Example)

Also, we apply a sensitivity test for Airmod by comparing the reference method at each time point and calculating the absolute deviations in breaths per minute (bpm). As a measure of accuracy, absolute deviations were calculated as a percent of reference.

Percent absolute deviation were averaged for each subject yielding overall measures of accuracy. To evaluate the accuracy of Airmod, the individual percent absolute deviation was compared for each monitoring time point by subtracting ManCRR from AirRR and then averaged within subject. A paired t test was used to evaluate significance across subjects.

To measure the precision of Airmod for each subject, the standard deviation of percent deviations (in nonabsolute value) was calculated. The precision of Airmod was compared through a paired t test of the subject-specific standard deviations of Airmod's percent deviations from reference.

9.2.3 Analysis to evaluate the response time of the first breath detection followed by administration of jaw thrust during the apnea period. The 3rd secondary objective is to compare the response time of Airmod versus Capnography.

Use paired t-test to compare the response time of Airmod versus Capnography on Capnostream[™]35 after administration of jaw thrust. The target of p<0.05 indicates significance difference.

Evaluating the Non-Inferiority of Airmod to Capnostream™35 on Respiratory Rate Monitoring and User Experience Clinical Evaluation

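### The protocol calls agreement acceptable when differences fall inside limits computed from those same differences, a rule that carries no information about how large they are

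*Protocol*

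**What the plan says.** Secondary endpoint 2 measures agreement between AirRR and ManCRR by a concordance correlation coefficient and a Bland-Altman analysis. The endpoint statements in protocol 1.1 and 3 and SAP 4.4 give no pass mark. The protocol's analysis section adds one: if the differences in respiratory rate from the "two equipment are in the 95% LoA, we will say that RR measured from these two equipment are correlated and acceptable" (protocol 9.4.3, item 2).

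On the construction of the plot and limits:

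- Protocol 9.4.3 plots the mean of the two measurements on the x-axis and "the difference between the two values as the y-value".
- SAP 8.2.5 says that "the two LoA are the mean value of x separately ±1.96SD". It also mentions repeatability, in the words "To compare an estimate of this to the LoA", without saying what result would pass.
- SAP 9.2.2 says "Bland Altman analysis, and concordance correlation is adopted to measure the agreement between AirRR and ManCRR", and gives no acceptance limit.
- SAP section 9 gives interval levels for this analysis, "99.69% CI at interim analysis and 95.1% at final analysis of the difference between DUTs in an unit difference plot", again with no limit.

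The 3 and 2 bpm margins belong to other analyses. M1, for example, "indicates non-inferiority at margin of 3 bpm (M1) and sampling rate 1Hz" under secondary endpoint 4. They are not applied to the limits of agreement.

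**The concern.** Limits of agreement describe how far apart two methods are. They become a criterion only when set against a limit that comes from outside the data. Here the differences are judged against an interval calculated from themselves. A device with errors of 1 bpm and one with errors of 10 bpm would be treated alike, and lying inside the limits says nothing about correlation.

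The primary test is one-sided and concerns the mean difference, so positive and negative errors can cancel in it. Endpoint 2 is where the scatter of individual readings should be judged. If the sentence is followed, the report may call the two measures correlated and acceptable with nothing behind either word.

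**Working it through.** **Inputs.** Limits: mean ±1.96 SD (SAP 8.2.5, read as the mean and SD of the differences). Planned enrolment: 300, with an interim look at 150 (protocol 9.2 and 9.4.6). Pilot SD: "σ=3.29647" from 25 cases (SAP 9.1, Table 6).

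**1. The plan's 95%.** For normal differences the coverage is 2Φ(1.96) − 1 = 0.9500, so the label reproduces.

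**2. Dependence on spread and bias.** Replace each difference d by a + b·d, with b > 0. The mean becomes a + b·mean and the SD becomes b·SD. The quantity |d − mean|/SD is unchanged, and so is the share with |d − mean| ≤ 1.96 SD. The share depends on the shape of the distribution, never on its scale or centre.

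Numerical check on one fixed normal sample of 300, rescaled:

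| SD multiplier (bpm) | Bias added | Limits (bpm) | Inside own limits | Within ±3 bpm |
|---|---|---|---|---|
| 0.5 | 0 | −0.96 to 0.85 | 93.7% | 100% |
| 3.29647 | 0 | −6.30 to 5.63 | 93.7% | 72.7% |
| 20 | 0 | −38.24 to 34.13 | 93.7% | 14.3% |
| 1 | 5 | 3.09 to 6.71 | 93.7% | 2.3% |

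A heavier-tailed sample (t, 4 df) gave 94.3% throughout. The share within a fixed ±3 bpm moves with accuracy; the share inside the sample's own limits does not.

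**3. What the rule would decide.** The sentence does not say what share must be inside. In 20,000 simulated normal samples at each size:

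| Reading | n = 150 | n = 300 |
|---|---|---|
| Average share inside | 95.1% | 95.1% |
| Samples with all inside | 0 | 0 |
| Samples with at least 95% inside | 53% | 61% |

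A loose reading is met, a literal reading fails, and a strict 95% cut is close to a coin toss. By step 2, none of these results depends on the spread. The simulation treats differences as independent. Repeated readings within a subject change how the SD should be estimated, but not the scale invariance.

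**4. Scale, as illustration only.** Table 6 does not say what 3.29647 is the SD of.

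- If it is the SD of the paired differences, with zero bias and normality: 1.96 × 3.29647 = 6.46 bpm. The share within ±3 bpm is 2Φ(3/3.29647) − 1 = 0.637, so 36% are off by more. Within ±2 bpm it is 0.456, so 54% are off by more.
- If it is a single-device SD, equal for both methods, with correlation ρ: SD of the difference = 3.29647 × √(2(1 − ρ)), and the limits are ±1.96 times that.

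| ρ | SD of difference | Limits (bpm) |
|---|---|---|
| 0 | 4.662 | ±9.14 |
| 0.5 | 3.296 | ±6.46 |
| 0.8 | 2.085 | ±4.09 |
| 0.9 | 1.474 | ±2.89 |
| 0.95 | 1.042 | ±2.04 |

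These are very different devices, and the rule treats them all alike.

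**The case against.** The best defence is that this is one explanatory sentence. The formal endpoint only measures agreement, protocol 9.4 defers detail to the SAP, and the SAP does not repeat the rule. That stands, and it makes the repair small. But the sentence is current protocol text and the only decision rule that either document gives for this endpoint.

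A second defence is that the limits may not be self-referential. SAP 8.2.5 refers to the mean of x, and treats AirRR and CapRR as separately compared with ManCRR. Limits built from CapRR–ManCRR and applied to AirRR–ManCRR would not be circular. The wording is indeed unclear, but no text states such a rule.

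Third, a reader might infer that nothing else in the plan would reveal poor minute-by-minute performance. That is not so. SAP 8.2.6 plans a repeated-measures concordance coefficient with a 95% interval. SAP 8.2.7 plans Tukey outliers and a box plot of the AirRR–ManCRR differences. SAP 9.2.2 plans percent absolute deviations and a within-subject SD of percent deviations. Scatter would therefore be reported. None of these has an acceptance limit, so none supports the word acceptable.

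Fourth, a reader might conclude from the pilot SD that the device would fail a ±3 bpm limit. The documents do not support that: at a correlation of 0.9 on the single-device reading, the limits are ±2.89 bpm.

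**Conclusion.** The concern holds. As written, the rule cannot distinguish good agreement from poor, and cannot show correlation. This rests on the ordinary reading that the limits come from the differences being judged. It does not rest on the pilot SD, the sample size or normality: a different distribution shape would change the 95%, but not its indifference to spread and bias.

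The rule is uninformative, but it is not guaranteed to pass; that depends on what share inside is required, which the protocol does not say. The ±6.46 bpm, 36% and 54% figures are one scenario, and the possible limits run from ±9.14 to ±2.04 bpm across the single-device correlations shown. Nor do the documents make M1 or M2 the natural ceiling for the limits of agreement: protocol 9.4.3 item 4 sets both as margins for bias.

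This should be fixed, but it concerns a secondary endpoint. The primary non-inferiority test has its own margin and does not use this sentence.

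**What to change.** Delete the sentence from protocol 9.4.3 item 2 and make the endpoint descriptive. Report:

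- the bias and the limits of agreement in repeated-measures form (the protocol's reference 20 is already a method for multiple observations per individual), with confidence intervals;
- the percentage of readings within ±2 and within ±3 bpm of ManCRR.

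Mirror this in SAP 8.2.5 and 9.2.2. In 8.2.5, centre the limits on the mean difference instead of the mean of x, and state which pair of measures each set of limits describes.

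If the sponsor wants a conclusion of acceptability, it should fix and justify its own maximum limits of agreement in bpm before the data are seen. That limit need not be M1 or M2.

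The cost is wording and a little programming, on data the plan already collects, with no effect on sample size or conduct. The downside is that the report loses an automatic statement that agreement is acceptable. If a limit is set, the endpoint can fail.
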